8.6.2 Statistical Methods for Safety Analyses

Safety and tolerability will be assessed by clinical review of all relevant parameters including adverse experiences (AEs).

The analysis of safety results usually follow a tiered approach in the studies conducted by the SPONSOR. However, this study has only 1 treatment group. Thus, the following summaries will be provided as described in [Table 6](#).

- Incidence is defined as (number of subjects with the indicated endpoint divided by the total number of subjects with follow-up over the relevant period)*100%.
- For the measured adverse experiences of redness and swelling, 0 to 1 inch will be categorized as mild intensity, >1 inch to 2 inches will be categorized as moderate intensity, and >2 inches will be categorized as severe intensity

The specific events of interest in this study will be injection-site adverse experiences prompted for on the VRC, such as pain/tenderness, swelling and redness occurring Day 1 through Day 5 following any vaccination, and elevated temperature ($\geq 37.5^{\circ}\text{C}$), from Day 1 to Day 5 following any vaccination.

Table 6 Analysis Strategy for Safety Parameters

Adverse Experience Endpoint	Follow-Up Period		
	After Any Vaccination Visit		Any Time During Study
	Day 1 to Day 5 [†]	Day 1 To Day 15 [†]	
Clinical AEs/vaccine-related AEs			
Any AE/vaccine-related AE		•	•
Deaths			•
Injection site AEs/vaccine-related AEs			
AEs/vaccine-related AEs of pain/tenderness, swelling, and redness	•		
Other injection site AEs/vaccine-related AEs	•		
Severe injection site AEs [§] /vaccine-related AEs	•		
Number (%) of subjects by maximum intensity rating, over all injection site AEs [§] /vaccine-related AEs	•		
Number (%) of subjects by maximum intensity rating, within each of the categories of injection site AEs [§] /vaccine-related AEs	•		
Systemic AEs/vaccine-related AEs			
Systemic AEs/vaccine-related AEs		•	
Number (%) of subjects by maximum intensity rating, over all systemic AEs/vaccine-related AEs		•	
Temperatures			
Elevated temperatures [#]	•		
Maximum temperatures ^{††}	•		
AEs of Special Interest			
Serious AEs		•	
Serious vaccine-related AEs			•
New medical conditions ^{**}			•
[†] The day of vaccination is counted as Day 1. Day 1 to Day 5 refers to the period within 4 days of a vaccination. Day 1 to Day 15 refers to the period within 14 days of a vaccination. [§] For the measured adverse experiences of redness and swelling 0 to 1 inch will be categorized as mild, >1 inch to 2 inches will be categorized as moderate and >2 inches will be categorized as severe. [#] Defined as maximum (over the follow-up period) temperature $\geq 37.5^{\circ}\text{C}$. ^{††} Distribution of maximum temperatures over the relevant follow-up period. ^{**} Including new medical conditions considered potentially of an autoimmune nature. AEs = Adverse experiences;			

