7.1.2.2 Vaccination Report Card (VRC)

Each subject will receive a VRC at the study vaccination visit. On the VRC, the parent/guardian of the subject will be asked to record his oral temperature in the evening after each study vaccination and daily for 4 days after each study vaccination for the purpose of identifying febrile events. Also, beginning after each study vaccination and for a total of 15 days including the day of vaccination, the parent/guardian of the subject will be asked to record injection-site and systemic adverse experiences, concomitant medications, and concomitant vaccinations on the VRC. The information on VRC should be generated only by the parent/guardian of the subject and must be signed and dated by the subject's parent or guardian to confirm the accuracy of the recorded information. The subject's parent or guardian will be asked to bring the VRC to the study site at the next scheduled visit.

When the VRC is returned, the VRC should be reviewed for completeness by study site personnel. If clarification is needed, the study site personnel will discuss the VRC with the subject's parent/guardian. Original information on the VRC should never be altered by study personnel, although comments can be written in the designated area for study site personnel on the front of the VRC. Corrections to the VRC can only be made by the subject's parent/guardian. Any corrections to the VRC should be made by using an ink pen to add the omitted data and/or to draw a single line through the error and add the correct information. The subject's parent/guardian should initial/date all VRC corrections.

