8.1 Statistical Analysis Plan Summary

Key elements of the statistical analysis plan are summarized below; the comprehensive plan is provided in Sections 8.2-8.12.

Study Design Overview	A phase III, open-label, clinical trial to study the safety and immunogenicity of the quadrivalent HPV (Types 6, 11, 16, 18) L1 VLP Particle (VLP) vaccine in 9- to 15-year-old boy
Treatment Assignment	Subjects meeting inclusion/exclusion criteria will be allocated to V501.
Analysis Populations	Immunogenicity: Per-Protocol Immunogenicity (PPI) Safety: All Subjects as Treated (ASaT)
Primary Endpoint(s)	Primary immunogenicity endpoint will be seroconversion rate for the vaccine HPV types (6, 11, 16 and 18) at 4 weeks post dose 3.
Key Secondary Endpoints	Key secondary endpoint includes cLIA geometric mean titers (GMTs) for the vaccine HPV type (6, 11, 16 and 18) at 4 weeks post dose 3.
Statistical Methods for Key Efficacy/Immunogenicity/ Pharmacokinetic Analyses	The primary hypothesis with respect to anti-HPV 6, 11, 16 and 18 seroconversion percentages by 4 weeks post dose 3 will be evaluated by computing point estimates and constructing 95% confidence interval. (The success criterion for the primary analysis requires that point estimates for seroconversion rate be greater than 90% for all 4 vaccine HPV types.) The secondary hypothesis will be evaluated by comparing anti-HPV 6, 11, 16 and 18 GMTs at 4 weeks post dose 3 in 9- to 15-year-old boys from this study with those in 16- to 26-year old young men (all young men who were vaccinated by V501 and met the per-protocol immunogenicity criteria of PN122 will be included) by constructing a 95% confidence interval for the ratio of GMTs.

Statistical Methods for Key Safety Analyses	The adverse experiences of interest in this study include injection site adverse experiences/vaccine-related adverse experiences prompted for on the VRC occurring Day 1 through Day 5 following any vaccination, systemic adverse experiences/vaccine-related adverse experiences reported Day 1 through Day 15, elevated temperatures from Day 1 to Day 5 following any vaccination. Summary tables will be provided.
Interim Analyses	The immunogenicity and safety analysis of Day 1 through Month 7 will be performed after the data through Month 7 have been declared final and complete. The analysis of Month 18 through Month 30 immunogenicity and safety data will take place at the end of the study.

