8.4.2 Safety Endpoints

Safety assessment will focus on the injection site adverse experiences/vaccine-related adverse experiences and elevated temperatures on Days 1 to 5 post-vaccination, and systemic adverse experiences/vaccine-related systemic adverse experiences on Days 1 to 15 post-vaccination, reported on the Vaccination Report Card (VRC). Serious adverse experiences reported Days 1 to 15 post-vaccination, vaccine-related serious adverse experiences reported any time during the study and new medical condition occurring any time during the study will also be summarized.

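### Injection-site events are recorded for 15 days after each dose but summarised only to Day 5, so a late local reaction enters no injection-site incidence

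*Combined protocol and SAP*

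**What the plan says.** **Collection.** Section 7.1.2.2 states that, on the Vaccination Report Card (VRC), "for a total of 15 days including the day of vaccination, the parent/guardian of the subject will be asked to record injection-site" events, along with systemic ones. Section 7.2 separately requires the investigator to report all AEs through 14 days after each vaccination. With the day of vaccination counted as Day 1 (Table 6 footnote), that is Days 1–15. Section 4.2.3.2 differs: it has the VRC collect local AEs for 5 days and systemic AEs for 15.

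**Endpoints.** Section 8.4.2 focuses on "injection site adverse experiences/vaccine-related adverse experiences and elevated temperatures on Days 1 to 5 post-vaccination" and on systemic events on Days 1–15. It does not limit the local window to prompted reactions. Two other places are narrower: Section 8.1 describes the injection-site events of interest as those "prompted for on the VRC occurring Day 1 through Day 5 following any vaccination", and the text of Section 8.6.2 names "injection-site adverse experiences prompted for on the VRC, such as pain/tenderness, swelling and redness occurring Day 1 through Day 5 following any vaccination".

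**Table 6.** All five injection-site rows are marked for Day 1–5 only. They are the row for pain/tenderness, swelling and redness; "Other injection site AEs/vaccine-related AEs"; the severe row; "Number (%) of subjects by maximum intensity rating, over all injection site AEs"; and the matching row within each category. Both systemic rows are marked for Day 1–15. The row "Any AE/vaccine-related AE" is marked for Day 1–15 and also for any time during the study.

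**Grading.** Table 2 in Section 7.2.3 grades redness and swelling by maximum size through Day 5.

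**The concern.** The summary window for local events is a third of the length of the period over which Sections 7.1.2.2 and 7.2 collect them, while systemic events from the same card are summarised over the whole period. The row for other injection-site AEs is by name the category outside the prompted reactions, yet it has the same short window as they do.

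That a 3-dose regimen is well tolerated is a primary objective (Section 3.1), and it has no statistical success criterion. The descriptive safety tables therefore carry the evidence. A local reaction that starts on Days 6–15 would be in the database, but a reader of the planned tables could not see it as an injection-site event.

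A smaller labelling matter concerns the any-time mark on the any-AE row. Section 8.6.2 defines incidence as a percentage of subjects followed over the relevant period, so the cell could be read as a 30-month incidence of all AEs. Collection does not support that reading.

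**Working it through.** **1. Where a late local event is counted.** Take a non-serious injection-site AE with onset on Days 6–15 after a dose.

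| Table 6 row | Window marked | Counts the event? |
|---|---|---|
| Five injection-site rows | Day 1–5 | No |
| Two systemic rows | Day 1–15 | No, the event is not systemic |
| Any AE | Day 1–15 and any time | Yes, pooled with all other AEs |
| Serious AE rows | Day 1–15; any time if vaccine-related | Only if serious |

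The event thus contributes to no injection-site incidence and has no injection-site intensity rating in the tables.

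**2. Days covered.** Recorded days per dose: 15. Summarised in the injection-site rows: 5. Not summarised there: 15 − 5 = 10. Over three doses this is 3 × 10 = 30 of 3 × 15 = 45 days. These are days, not events; Section 4.2.3.2 says that most AEs occur within a few days of vaccination, so the share of events is smaller.

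**3. The plan's own safety figures.** Section 8.9.3 gives a 63% chance of seeing at least one event among 100 subjects at a true incidence of 1%: 1 − 0.99^100 = 0.634, which agrees. With no events in 100 it gives an 80% upper bound of 1.6%: 1 − 0.20^(1/100) = 1.597%, which also agrees. Neither figure is in question.

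**4. How many boys might be affected.** The documents give no rate of late local reactions. Let p be an assumed share of the 100 subjects with one. The expected number is 100p, and the chance of at least one is 1 − (1 − p)^100.

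| Assumed p | Expected subjects | Chance of at least one |
|---|---|---|
| 1% | 1 | 63% |
| 2% | 2 | 87% |
| 5% | 5 | 99% |

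**5. Can the any-AE row reveal them?** Incidence counts each subject once. Let f be an assumed share of subjects who have another AE within the Day 1–15 windows, independently of a late local reaction. The late reactions then add 100p(1 − f) subjects to the row.

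| Assumed f | p = 2% | p = 5% |
|---|---|---|
| 0.5 | 1.0 | 2.5 |
| 0.7 | 0.6 | 1.5 |
| 0.9 | 0.2 | 0.5 |

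Even the subjects who are added are not identified as having a local reaction, so the injection-site figure cannot be recovered from this row.

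**6. The any-time cell.** Full AE reporting covers at most 45 days of about 30 × 30 = 900 (the flow chart takes a month as 30 days), which is 5%. The last window closes 14 days after dose 3. The Month 7 visit falls 21 to 49 days after dose 3, so Period II has no days of full AE reporting. Outside the windows, Section 7.2.2.1 still requires reporting of deaths and of serious AEs judged vaccine-related, and both have their own any-time rows. Later non-serious conditions are collected as new medical history (Section 7.1.1.4) and have their own row too; Section 8.4.2 says that "new medical condition occurring any time during the study will also be summarized". Section 7.2 also makes some AEs before allocation reportable. The cell is therefore the in-window AEs plus a few selected event types.

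**The case against.** The strongest reply is that the window is stated, reasoned and applied consistently. Section 8.4.2 sets Days 1–5 for injection-site events in general, Table 6 follows it, and Section 4.2.3.2 gives the reason that most AEs come early. Recording for longer than one summarises is not in itself a contradiction. This stands, and it rules out one tempting inference: a reader might conclude that Table 6 wrongly stretches a window meant only for prompted reactions over four of its five injection-site rows. The documents do not support that, because the endpoint section has no such limit.

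The reply is also right about intensity. The footnote on the severe and maximum-intensity rows brings in size grading of redness and swelling, and Table 2 stops size grading at Day 5. Day 1–5 is therefore a coherent window for those rows.

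Nor are late events lost. They stay in the database and in the any-AE row, they reach the serious rows if serious, and Section 8.6.2 provides for clinical review of all relevant parameters.

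On the any-time cell, a reader might infer that the mark is an error because Section 8.4.2 does not list any AE as an any-time endpoint. That does not follow: Section 8.4.2 omits deaths as well, yet Table 6 has an any-time row for them, so the section is not a full list of rows. The plan nowhere claims that the cell is a complete 30-month incidence.

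What the reply does not answer is why other injection-site AEs, collected for 15 days, should have no 15-day incidence when systemic AEs have one. The early-onset reason applies to both. Nor does it resolve the 5-day and 15-day statements on recording local events.

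**Conclusion.** The point holds as a minor gap in descriptive safety reporting. Its core is the absence of a Day 1–15 incidence for other injection-site AEs and for injection-site AEs overall, together with the conflict between Sections 4.2.3.2 and 7.1.2.2. The Day 1–5 rows themselves are sound, and the any-time cell needs only a label.

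The conclusion rests on the 15-day collection in Section 7.1.2.2, which the reporting rule in Section 7.2 supports. How many boys it concerns is unknown: the late-reaction rates of 1% to 5%, the shares of 50% to 90% with another AE, and their independence are all assumptions made for illustration. No hypothesis, success criterion, sample size or power figure changes.

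**What to change.** - **Sections 8.4.2 and 8.6.2 (Table 6).** Keep all Day 1–5 rows. Add a descriptive Day 1–15 incidence for other injection-site AEs and for any injection-site AE. Show the intensity of events with onset on Days 6–15 separately, on the general scale of Table 2, because size grading ends at Day 5. Possible wording for Section 8.4.2: *The incidence of injection-site adverse experiences over Days 1 to 15 after vaccination will also be described, with separate intensity ratings for those that begin on Days 6 to 15.*
- **Sections 4.2.3.2 and 7.1.2.2.** Reconcile the 5-day and 15-day statements on recording local AEs, with Section 7.2 in view.
- **Table 6, any-AE row.** Keep the any-time mark and add a footnote: outside the 14-day post-dose windows the cell contains only events reportable under Sections 7.2 and 7.2.2.1 and is not a complete any-time incidence.

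The cost is a few table entries, one footnote and one aligned sentence. The data are already to be collected under Sections 7.1.2.2 and 7.2, and Section 8.0 lets analysis changes be documented in a supplemental SAP before final database lock.

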8.6.3 Summaries of Baseline Characteristics, Demographics, and Other Analyses

Baseline characteristics and demographic variables

Baseline characteristics and demographic variables will be summarized by the use of tables and/or graphs. The number and percentage of patients screened, enrolled, vaccinated and the primary reason for discontinuation will be displayed. Demographic variables, baseline characteristics and prior and concomitant therapies (relevant pre-injection day ranges for summarization will be 3 days for medications, 14 days for non-live virus vaccines and 28 days for live virus vaccines) will be summarized either by descriptive statistics or categorical tables.

Baseline HPV Status

A serum sample will be collected from all subjects at the Day 1 visit for the purpose of assessing baseline HPV serostatus to the 4-valent HPV L1 VLP vaccine HPV types (HPV 6, 11, 16 and 18). A subject will be considered seropositive to a given HPV type at Day 1 if the subject's anti-HPV titer is \geq the corresponding serostatus cutoff for that HPV type or seronegative to a given HPV type at Day 1 if the subject's anti-HPV titer is $<$ the corresponding serostatus cutoff for that HPV type. For each HPV type, the proportions of subjects who are seronegative or seropositive will be summarized.

8.7 INTERIM ANALYSES

The immunogenicity and safety analysis of Day 1 through Month 7 will be performed after the data through Month 7 have been declared final and complete. The analysis of Month 18 through Month 30 immunogenicity and safety data will take place at the end of the study.

8.8 MULTIPLICITY

For the primary hypothesis, no multiplicity adjustment is necessary since success requires the observed seroconversion rates for all 4 vaccine HPV types to be greater than 90%. Similarly, for the secondary hypothesis for comparing GMTs in 9- to 15-year-old boys with those in 16- to 26-year old Japanese men, success is required on all 4 vaccine HPV types. Therefore, no multiplicity adjustment will be necessary to account for the multiple HPV types. The secondary hypothesis will only be tested if the primary hypothesis is demonstrated successfully.

8.9 SAMPLE SIZE AND POWER CALCULATION

8.9.1 Sample Size for Estimating Immune Response

Seroconversion percentage by Month 7

This study will enroll 100 subjects to receive V501, and will allow estimation of seroconversion percentage among subjects receiving V501 with a 95% confidence interval with a half-width of approximately 5 percentage points. This is based on the following assumptions: 1) an approximately 5% dropout and/or protocol violation rate, 2) an underlying response rate of 95% in the study population. Previously conducted studies of V501 indicate the seroconversion percentage is approximately 100%. For reference, seroconversion percentages (95% confidence intervals) were 97.5% (91.3, 99.7), 98.8% (93.2, 100), 98.8% (93.4, 100) and 98.8% (93.4, 100) for HPV 6, 11, 16 and 18, respectively, in Japanese girls (PN028). The calculation is based on the exact binomial method proposed by Clopper and Pearson (1934) with 95 subjects in the population expected to be included in the analysis, and is carried out using SAS ver. 9.2. [Table 7](#) summarizes estimates of probability that the point estimates of seroconversion percentage on 4 HPV types exceed 90%.

Table 7 Probability for Primary Immunogenicity Objective

True seroconversion percentage	Probability that the point estimate exceeds 90% for a specific HPV type	Probability that the point estimates exceed 90% for all 4 HPV types
95%	0.98	0.92
99%	> 0.99	> 0.99

The criterion requires that the point estimates of seroconversion percentage exceed 90%.

GMT at Month 7

This study will allow estimation of GMT among subjects receiving V501 with a 95% confidence interval with a half-width of 0.24 (ln mMU/mL) on the natural log scale (equivalently 1.27 fold on the original scale). The precision is based on the following assumptions: 1) an approximately 5% dropout and/or protocol violation rate, and 2) a SD of the natural-log-transformed titers of 1.2.

8.9.2 Sample Size for comparing immune response between 9- to 15-year-old boys and 16- to 26-year-old Young men

Table 8 summarizes the probability calculations for various true GMT ratios. The probability shown in the table is for meeting the secondary immunogenicity hypothesis in all 4 HPV types for 9- to 15-year-old boys vs. 16- to 26- year-old young men (all young men who were vaccinated by V501 and met the per-protocol immunogenicity criteria of PN122). The probability is based on the following assumptions: 1) an approximately 5% dropout and/or protocol violation rate in 9- to 15-year-old boys, 2) an approximately 40% of subjects are excluded from 550 young men vaccinated by V501 from PN122, 3) a margin of 2-fold, and 4) a standard deviation of 1.2 on the log scale (ln(mMU/mL)). The calculation is based on the t-test at alpha=0.025 (one-sided) with 95 boys and 400 young men expected to be included in the analysis and is carried out using SAS ver. 9.2. As shown in Table 8, this study will have more than 99% probability that the lower bounds of 95% confidence interval exceed 0.5 for all 4 HPV types given the underlying true GMT ratio is 1.0.

Table 8 Power for Secondary Immunogenicity Objective (9- to 15-Year-Old Boys vs. 16- to 26-Year-Old Young men)

True GMT Ratio	Probability that 95%CI lies above 0.5 for a specific HPV type	Probability that 95%CI lies above 0.5 For all 4 HPV types
1.0	>0.99	>0.99
1.5	> 0.99	> 0.99

The statistical criterion requires that the lower bound of two-sided 95% confidence interval of GMT ratio (boys vs. young men) being greater than 0.5.

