3.2 Secondary Objective(s) & Hypothesis(es)

- (1) **Objective:** To demonstrate that administration of V501 induces non-inferior geometric mean titers (GMTs) for serum anti-HPV 6, 11, 16 and 18 at 4 weeks post dose 3 in Japanese boys aged 9- to 15-year-old compared with those in Japanese men aged 16- to 26-year-old in Phase III study (Protocol 122) for V501 at 4 weeks post dose 3.

Hypothesis: V501 generates anti-HPV 6, 11, 16 and 18 GMTs 4 weeks post dose 3 in Japanese boys aged 9- to 15-year-old that are non-inferior to those in Japanese men aged 16- to 26-year-old. (The statistical criterion for success requires that the lower bound of two-sided 95% confidence interval of GMT ratio between boys enrolled in V501-200 and men enrolled in the Phase III study V501-122 be greater than 0.5 for each HPV type.)

- (2) Objective: To describe the persistence of the serum antibody titers for the vaccine HPV types 24 months following the third dose of V501.
- (3) Objective: To estimate the immune response for the vaccine HPV types (6, 11, 16 and 18) at 4 weeks post dose 3 using GMTs.

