Multiplicity	For the primary hypothesis, no multiplicity adjustment is required since success requires the observed seroconversion rates for all 4 vaccine HPV types to be greater than 90%. Similarly, for the secondary hypothesis for comparing GMTs between 9- to 15-year-old boys and 16- to 26-year old young men, success is required on all 4 vaccine HPV types. Therefore, no multiplicity adjustment will be made to account for the multiple HPV types. The secondary hypothesis will only be tested if the primary hypothesis is demonstrated successfully.
Sample Size and Power	This study will enroll 100 subjects to receive V501, and will allow estimation of seroconversion percentage with a 95% confidence interval with a half-width of approximately 5 percentage points to assess the primary objective. Given the true seroconversion percentage of 95%, there is 92% probability that the point estimates are greater than 90% for all 4 vaccine HPV types. This is based on the assumption of an approximately 5% dropout and/or protocol violation rate. For the secondary hypothesis, a sample size of 95 boys from this study and 400 young men from PN122 has more than 99% probability that the lower bounds of 95%CI exceed 0.5 for all 4 HPV types given the underlying true GMT ratio is 1.0. This is based on the following assumptions for young men from PN122 in addition to that for boys described above: no general protocol violation of 95%; exclusion rate due to Day 1 seropositive or PCR positive between Day 1 and Month 7 to HPV 6, 11, 16, and 18 is approximately 15%; 90% of randomized subjects completed vaccination phase.

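### Does the >0.99 stated for the secondary GMT comparison overstate its chance of success, given that the test is run only after primary success?

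*Combined protocol and SAP*

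**What the plan says.** Section 3.2 sets the criterion for the secondary hypothesis: "The statistical criterion for success requires that the lower bound of two-sided 95% confidence interval of GMT ratio", boys over men, be above 0.5 for each HPV type. It attaches no further condition.

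Section 8.8, and the Multiplicity row of the 8.1 summary, fix the testing order: "The secondary hypothesis will only be tested if the primary hypothesis is demonstrated successfully". Primary success means that all four seroconversion estimates exceed 90%.

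Section 8.9.1 plans the primary analysis on "an underlying response rate of 95% in the study population", and Table 7 also shows a 99% row. The same section says earlier studies gave values near 100% and cites Japanese girls in PN028: "97.5% (91.3, 99.7), 98.8% (93.2, 100), 98.8% (93.4, 100) and 98.8% (93.4, 100) for HPV 6, 11, 16 and 18". The Sample Size row of 8.1 repeats the primary figure: "Given the true seroconversion percentage of 95%, there is 92% probability that the point estimates are greater than 90" percent for all four types.

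Section 8.9.2 introduces Table 8 with "The probability shown in the table is for meeting the secondary immunogenicity hypothesis in all 4 HPV types". Its listed assumptions are the boys' dropout and violation rate, the exclusions among PN122 men, the margin and the SD. It concludes that "this study will have more than 99% probability that the lower bounds of 95% confidence interval exceed 0.5 for all 4 HPV types" at a true GMT ratio of 1.0. Section 8.1 gives the same result for the limits clearing 0.5: "For the secondary hypothesis, a sample size of 95 boys from this study and 400 young men from PN122 has more than 99% probability".

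**The concern.** Under the testing order, the secondary hypothesis can be declared met only if two things happen: all four seroconversion estimates exceed 90%, and all four GMT-ratio limits exceed 0.5. The introductory clause of 8.9.2 speaks of meeting the secondary hypothesis, yet >0.99 is the probability of the second event alone. At the 95% seroconversion rate used for the primary calculation, the first event has probability 0.92, so the probability of both cannot be above 0.99.

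Section 4.2.1 makes this comparison the means of bridging efficacy from men to boys. A reader who took >0.99 as the overall chance of a successful bridge would put the risk of failure below 1%, when it would be about 8% at a 95% seroconversion rate. If the plan had claimed a power that its own testing order rules out, the sample size justification for the bridging aim would need correcting.

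**Working it through.** **1. Reproduce Table 8.** Inputs from 8.9.2: 95 boys, 400 men, SD 1.2 on the natural-log scale, margin 0.5, one-sided alpha 0.025, true ratio 1.0.

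- Standard error = 1.2 × √(1/95 + 1/400) = 0.137.
- Noncentrality = ln(1.0/0.5) / 0.137 = 0.693/0.137 = 5.06, with 95 + 400 − 2 = 493 degrees of freedom.
- Power from the noncentral t distribution = 0.9990 per type.
- All four types, multiplied as if independent: 0.9990⁴ = 0.9960.
- At a true ratio of 1.5, both values exceed 0.9999.

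Both rows of Table 8 reproduce for the event that all four limits exceed 0.5.

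**2. Reproduce Table 7.** Inputs from 8.9.1: 95 evaluable boys and a point estimate above 90%. Since 0.90 × 95 = 85.5, at least 86 must seroconvert.

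- At 95%: P(X ≥ 86) = 0.9795 per type; 0.9795⁴ = 0.9204.
- At 99%: above 0.9999 per type and for all four.

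These match the printed 0.98, 0.92 and >0.99. The step from 0.98 to 0.92 shows that the plan multiplies across types as if they were independent.

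**3. Combine the two.** Treating the two stages as independent as well, at ratio 1.0:

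| True seroconversion | Primary met, all 4 | Limits > 0.5, all 4 | Both |
|---|---|---|---|
| 95% | 0.9204 | 0.9960 | 0.917 |
| 96% | 0.981 | 0.9960 | 0.977 |
| 97% | 0.998 | 0.9960 | 0.994 |
| 99% | >0.9999 | 0.9960 | 0.996 |
| PN028 rates (97.5, 98.8, 98.8, 98.8%) | 0.9999 | 0.9960 | 0.996 |

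At ratio 1.5 and 95% the product is 0.920. The joint probability reaches 0.99 at a true rate of about 96.6% for ratio 1.0.

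**4. Sensitivity to dependence.** At 95% and ratio 1.0:

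- Lower bound under any dependence: 1 − 4(1 − 0.9795) − 4(1 − 0.9990) = 0.914.
- Upper bound: the smaller of 0.9795 and 0.9990, that is 0.979.

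If the four types were fully dependent, 0.99 would be reached from a true rate of about 95.5% instead of 96.6%. The same boys supply all four titres, and HPV 6 and 11 share one per-protocol population (Section 8.5.1), so some positive dependence is plausible.

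**5. Which event does the plan name?**

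- Table 8, both probability columns: the confidence interval lies above 0.5.
- Table 8, footnote: the lower limit of the GMT ratio is above 0.5.
- Section 8.9.2, closing sentence, and Section 8.1: the lower limits exceed 0.5 for all four types.
- Section 3.2: the secondary criterion is that same condition and nothing else.
- Section 8.9.2, assumptions: no seroconversion rate, so the figure cannot be meant to include the primary result.

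The introductory clause uses the hypothesis as 3.2 defines it. Every place that spells out the event gives the one computed in step 1.

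**6. Can the reader see the restriction?** In 8.1 the testing order stands in the Multiplicity row. The next row gives 92% for the primary and then >99% for the secondary. Section 8.8 repeats the order immediately before 8.9, and Table 7 comes before Table 8. Section 8.6.1 also makes success of the study depend on the primary criterion.

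**The case for a change.** The strongest counter-argument keeps to the plan's own 95% rate. There, no form of dependence lifts the joint probability above 0.979, because a single type passes the primary criterion with probability only 0.9795. The shortfall is therefore not a product of the independence assumption. The joint figure is printed nowhere, Section 8.9.2 read alone does not mention the testing order, and bridging is the stated purpose of the trial. In 8.1 the secondary sentence also follows directly on one that assumes 95%.

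The arithmetic stands: at 95% the joint probability is about 0.92. What does not follow is that a stated figure is wrong. The plan nowhere says that >0.99 includes the primary result, nor does it promise a joint probability. The boys' assumption that 8.1 carries over to the secondary calculation is the 5% dropout and violation rate; the 95% rate belongs to the primary statement. Giving power for each hypothesis separately and stating the order of testing beside it is an ordinary way to present a fixed sequence. Both factors are printed, and the risk of stopping at the primary stage is the 0.92 in Table 7. A label on Table 8 would be harmless, but it would tell the reader nothing that 8.1 does not already show.

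One discrepancy nearby has no bearing on this: excluding 40% of 550 men leaves 330, whereas the factors in 8.1 give 550 × 0.95 × 0.85 × 0.90 = 400. With 330 men, the all-four power at ratio 1.0 is 0.994, still above 0.99.

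**Conclusion.** The concern does not hold. The >0.99 is correct for the event that Table 8, Section 8.1 and Section 3.2 define: 0.996 at a true GMT ratio of 1.0 and above 0.9999 at 1.5, with 95 boys, 400 men, SD 1.2 and types treated as independent. The testing order and the 92% are disclosed beside it.

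The probability that both hypotheses succeed is a different quantity. At ratio 1.0 it is about 0.917 if true seroconversion is 95% (0.914 to 0.979 over all forms of dependence). It is 0.996 at 99% and at the PN028 rates, so >0.99 holds even with the primary criterion included at the rates that the plan's cited experience supports. It falls below 0.99 only for true rates under about 96.6% with independence, or about 95.5% with full dependence. Analyses, success criteria, type I error and the enrolment of 100 boys are the same on either reading.
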